	2	If persist: phenylephrine 100 mcg (max. 300 mcg)		If persist: labetalol 5 mg (max. 15 mg)
	3	If persist: reduce infusion of study drug by 50%		If needed, hydralazine 5 mg (max. 20 mg)
Tachycardia > 100 bpm	1	Desflurane decrease by 50% to a min. of 2%	Desflurane increase by 50% to a max. of 8%	Desflurane increase by 50% to a max. of 8%
	2	If persists: phenylephrine 100 mcg (max 300 mcg)	If persists: labetalol 5 mg (max 15 mg)	If persists: labetalol 5 mg (max. 15 mg)
	3	If persists: reduce infusion of study drug by 50%	If persists: give fentanyl 50 mcg boluses	If persists: give fentanyl 50 mcg boluses

Minimum mean arterial blood pressure = 55 mmHg

VI. Surgery Conclusion

Anesthetic and study drug infusion will be discontinued at skin closure. Patients will be extubated in the operating room and transferred to the PACU. VRS pain scores will be collected immediately upon arrival. The anesthesiologist will decide which postoperative pain medications to administer, but must use a standardized computer order set in CS-link. This set gives the option of using the following opiates: hydromorphone IV, fentanyl IV, or acetaminophen-hydrocodone PO. Ondansetron 4 mg IV will be given for nausea and vomiting. VRS pain scores will be measured again prior meeting PACU discharge criteria (awake and alert with stable vital signs and the absence of intractable side effects)

VII. Postoperative Period

- a. After PACU discharge, pain control will be assumed by the primary surgical team or inpatient pain service. Pain medication regimens commonly include PRN dilaudid IV and oral narcotics e.g., percocet (oxycodone/acetaminophen) or norco (hydrocodone/acetaminophen). Thus, patients will always receive some form of narcotic as a part of their pain medication regimen.

PATIENT DATA COLLECTION

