- I. Preoperative demographics: age, weight, BMI, gender, ASA status, race, preoperative medications including beta-blockers and Lidoderm patches, prior back surgery, prior pain procedures, past medical/surgical history, social history (smoking, drinking, illicit drug use) allergies, history of postoperative nausea and vomiting, history of motion sickness and short-form 12 (SF-12) score after completing the survey. Name, phone number, e-mail address, and medical record number will be collected and stored in a secured separate file to prevent bias and inadvertent unblinding. Only the study coordinator will have access to this file and the patient will be referred to solely by subject number.
- II. Preoperative data: baseline VRS pain score, vital signs (blood pressure, heart rate, temperature, respiratory rate, oxygen saturation via pulse oximetry), 12-lead EKG interpretation, duration of pain, any abnormal lab results, additional surgical procedures (e.g., fusion, discectomy), and number of levels.
- III. Intraoperative data:
 - Vital signs (including blood pressure, heart rate), BIS values, every 5 – 10 minute intervals
 - dosages of all medications given (anesthetics, analgesics, local anesthetics, rescue medications, adjuncts such as decadron, end-tidal desflurane concentration, rate of propofol infusion), IV fluids, blood products, colloids, blood loss, urine output
 - Duration of surgery (from skin incision to closure), duration of anesthesia (from IV induction until anesthetic drug discontinuation)

IV. Postoperative data:

- Time on arrival to PACU, departure, and total length of stay
- VRS pain score and nausea on arrival to the PACU, vital signs, opiate and antiemetic requirements in the PACU
- PACU complications such as respiration depression (respiratory rate < 8, need for naloxone, or respiratory arrest), hypoxemia or desaturation ($\text{SpO}_2 < 90\%$ or need of supplemental oxygen to maintain $\text{SpO}_2 > 95\%$), hypotension, cardiac arrhythmias, myocardial infarction, nausea and vomiting, respiratory distress.
- Total opioid, adjuvant (e.g., anticonvulsants, antispasmodics, SSRI's) and antiemetic consumption at 24, 48, and 72 hours following surgery. If patients are discharged from the hospital prior to 72 hours, a telephone interview will be conducted to determine opioid/adjuvant consumption at home.

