- VRS pain scores, vital signs and medication side effects (e.g., ketamine-induced hallucinations) at 24, 48, and 72 hours following surgery; time to return of daily activities (oral diet, return of bowel function, ambulation, showering) in days, any complications such as cardiac arrhythmias, global evaluation of anesthesia experience with 0 = worst, 10 = best
- Length of hospital stay

V. 6 week post-surgical assessment data:

- VRS pain score, opioid/adjuvant consumption, medication side effects (e.g., hallucinations, constipation, nausea and vomiting), SF-12 score.

Note: all opioid consumption will be converted to morphine equivalents for data analysis and presentation.

DATA ANALYSIS

Sample size estimates were based on the test for inequality of opioid consumption among the methadone, ketamine, and ketamine + methadone groups. We expect to observe at least a 30% decrease in opiate consumption between ketamine + methadone group and methadone or ketamine. Prior studies demonstrated that the postoperative opioid consumption and its standard deviation for methadone and ketamine are quite similar (10, 21). Mean opioid consumption was approximately 67 mg \pm 38 mg (SD) for Menigaux's et al. ketamine group and median 63 mg (interquartile range, 27-86.1), which gives an estimated SD of 23. The expected group mean difference would be 18.9 for an approximate 30% decrease in opioid requirements. However, we would like to be more conservative in our study since the aforementioned study populations were most likely skewed. For a two-tailed hypothesis with alpha 0.05, we would need at least 38 subjects per group to achieve a power of 0.8 to detect a 30% reduction in opioid consumption.

Two group t-test of equal means (equal n's)

	1	2	3	4
Test significance level, α	0.050	0.050	0.050	0.050
1 or 2 sided test?	2	2	2	2
Group 1 mean, μ_1				
Group 2 mean, μ_2				
Difference in means, $\mu_1 - \mu_2$	18.900	20.000	17.000	15.000
Common standard deviation, σ	23.000	23.000	23.000	23.000
Effect size, $\delta = \mu_1 - \mu_2 / \sigma$	0.822	0.870	0.739	0.652
Power (%)	80	80	80	80
n per group	25	22	30	38

Similarly for VAS pain scores, previous studies found average scores to range from 2.8 ± 2.0 for methadone group and 5.4 ± 2.0 for the ketamine study (7, 10). With alpha 0.05, power 0.8 and mean difference of 1.6, each group needs at least 17 subjects to observe a 30% reduction in VAS pain scores.

Two group t-test of equal means (equal n's)

	1	2	3	4

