--	--	-----------------------------------------------------------------------------------------------------------------------	-----------------------------------------------------------------------------------------------------------------------------------------------------------------------------------------------------------------------------	----------------------------------------------------------	--------------------------------------------------------------

Methadone carries the same side effect profile as other opiates (constipation, mild drowsiness, pruritus, nausea and vomiting, miosis, respiratory depression), with two chief exceptions - prolonged qTc interval and long-half life. Previous studies suggest that doses as low as 30 mg/day can prolong qTc interval > 0.5 seconds and those who developed Torsades de Pointes (TdP) had doses as low as 40 mg/day (25). 3.6% of subjects receiving methadone developed (TdP) and had abnormal baseline EKG. Erhet et al. also determined that low serum potassium levels, lower serum prothrombin levels (indicative of poor liver function and thus, drug metabolism), and concomitant use of drugs with higher CYP3A4 inhibition were positively associated with prolonged qTc. For our study, we are excluding patients who are morbidly obese, with liver disease, on medications known to inhibit CYP3A4 and/or have arrhythmias in their preoperative EKG.

Since methadone has a half-life of approximately 24-36 hours (22), respiratory depression risk may be increased when additional sedatives are given. Thus, we are excluding any high-risk patients who have poor respiratory status (COPD, any restrictive lung disease, sleep apnea). Nursing will be advised to avoid oversedation. If the patient goes into respiratory depression i.e., respiratory rate < 8 breaths per minute, naloxone (0.1-0.2 mg every 2-3 minutes to keep respiratory rate > 8) can be administered. Supplemental oxygen will be provided to maintain oxygen saturation > 95% during these episodes.

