If the postoperative EKG demonstrates prolonged qTc interval of >470 ms for men and >480 ms for women OR a 60 millisecond (or 25%) increase from baseline, the patient will be placed on telemetry. Serum potassium and magnesium levels will be monitored closely and replaced as necessary. If the patient enters Torsades de Pointes and is hemodynamically unstable, prompt nonsynchronized electric defibrillation can be performed. A magnesium sulfate infusion will be started for treatment and prevention. If the patient does not respond to magnesium, transvenous overdrive pacing at 100 beats per minute will be instituted. Isoproterenol (starting at 2 mcg/min and titrating to heart rate of 100 beats per minute) can also be used as a temporizing measure while transvenous pacing is being setup.

The patient will be admitted to the critical care unit if they have hemodynamic instability, syncope, or ventricular ectopy, T wave alternans, AV block or QRS widening on their postoperative EKG.

In general, less likely and rare side effects are seen in higher than clinically acceptable doses or prolonged use of the drug. Those with co-existing diseases that increase the likelihood of the more rare and severe side effects such as increased intracranial pressure will be excluded. Ketamine has an elimination half-life of 3-5 hours while methadone's elimination half-life ranges from 24 – 36 hours (22). On average, lumbar laminectomy duration has been 2-3 hours. An additional 1-3 hours is spent in the PACU. Nausea and vomiting will be treated with an antinauseant such as ondansetron IV.

MANTAINANCE OF CONFIDENTIALITY

Patients' names will not be divulged and all data will be coded in the study records in accordance with standard HIPPA policy. Information gained during the course of the study will only be used by the investigators for the purpose of evaluating the effects of ketamine infusion with methadone during the intraoperative and postoperative period. All data will be coded in the study records. Copies of signed informed consent will be kept on file by the principal investigator, and no patient names or other identifying information will be used in any future publications.

SPECIAL PRECAUTIONS

All drugs will be used by an anesthesiologist who is familiar with them and trained to handle any untoward events related to medications

RISK-BENEFIT ASSESSMENT

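### The named respiratory depression and naloxone item covers only the PACU stay; later events rely on general adverse-event recording and daily readings

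*Combined protocol and SAP*

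**What the plan says.** Study Objective 2 is to compare side effects and hospital course between the combination and each drug alone. Data Analysis assigns side effects to chi-squared or Fisher's exact tests.

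In Patient Data Collection, IV, the respiratory item appears as "PACU complications such as respiration depression (respiratory rate < 8, need for naloxone, or respiratory arrest". A desaturation criterion follows in the same PACU list. Potential Risks gives the length of that stay: "An additional 1-3 hours is spent in the PACU".

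After the PACU, the plan has these general routes:

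- Summary of Study Design: adverse events are recorded on postoperative days one to three and at six weeks.
- Postoperative data: vital signs and medication side effects at 24, 48 and 72 hours (hallucinations are the example), and "any complications such as cardiac arrhythmias".
- Postoperative data: drug totals at 24, 48 and 72 hours for opioids, adjuvants and antiemetics. Naloxone is not named. For patients who go home before 72 hours, the telephone interview is described only for opioid and adjuvant use.

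On the timing of risk, Potential Risks states: "Since methadone has a half-life of approximately 24-36 hours (22), respiratory depression risk may be increased when additional sedatives are given". Methods VII says of the period after PACU discharge: "Pain medication regimens commonly include PRN dilaudid IV and oral narcotics", and concludes: "Thus, patients will always receive some form of narcotic as a part of their pain medication regimen".

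**The concern.** The one respiratory harm with an operational definition on the data list is tied to a place that patients leave within hours. The protocol's own account of methadone describes a risk that can outlast that stay while opioid treatment continues. Two of the three arms, 76 of 114 patients, receive methadone.

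At stake is the consistency of a safety outcome under Objective 2. If an event counts by rule in one setting and by someone's judgement in the next, the total by arm is not one endpoint. Pain and opioid use are followed in a structured way to 72 hours, and the named respiratory harm is not. The gap could hide harm. It could also hide benefit, since the Risk-Benefit Assessment expects fewer opioid-related side effects.

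**Working it through.** The plan states no figure for this point, so there is none to reproduce. The check compares the recording routes and then sizes the window.

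**1. One event in two settings.** Take a hypothetical patient whose respiratory rate falls to 6, who is given naloxone, and who then recovers.

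| Route | In the PACU | At 12 h, normal again by 24 h |
|---|---|---|
| Named respiratory item | Counts by definition | Does not apply |
| Vital signs at 24, 48, 72 h | Not needed | Normal reading, episode not seen |
| Drug totals at 24, 48, 72 h | Not needed | Naloxone not among the listed classes |
| Side effects, complications, adverse events | Also available | Recorded if someone reports it; no respiratory prompt and no stated look-back period |

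The later event can be recorded, but only through the last row. That the daily vital signs include respiratory rate and oxygen saturation is itself an inference, from the list given for the preoperative data.

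**2. Share of follow-up under the named item.** Input: PACU stay 1-3 h (Potential Risks).

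- First 24 h: 1/24 = 4.2%; 3/24 = 12.5%.
- 72 h: 1/72 = 1.4%; 3/72 = 4.2%.

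**3. Methadone remaining at PACU discharge.** Inputs: half-life 24-36 h; surgery 2-3 h ("On average, lumbar laminectomy duration has been 2-3 hours"); PACU 1-3 h; dose given before induction. Discharge is then 2 + 1 = 3 h to 3 + 3 = 6 h after the dose, ignoring induction and transfer time. Assuming single-exponential elimination, the fraction remaining is 0.5^(t / half-life).

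- Highest at discharge: 0.5^(3/36) = 0.94.
- Lowest at discharge: 0.5^(6/24) = 0.84.
- At 24 h: 0.5^(24/24) = 0.50 to 0.5^(24/36) = 0.63.
- At 72 h: 0.5^(72/24) = 0.125 to 0.5^(72/36) = 0.25.

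These are amounts remaining, not a respiratory hazard. They show only that the window closes while most of the dose is still present on the protocol's own half-life.

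**4. Effect on the comparison.** Let p be the true risk and c the share of events recorded, with M for a methadone arm and K for ketamine alone. The observed risk ratio is (c_M × p_M) / (c_K × p_K).

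- If c_M = c_K = c, the ratio is unchanged. The risk difference becomes c × (p_M − p_K), and precision falls because fewer events are counted.
- If p_M > p_K, the ratio is pulled down towards 1 only when c_M < c_K, that is, when the methadone arm's events fall disproportionately in the less well recorded period.

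The documents give no event times or rates, so c_M and c_K cannot be estimated.

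**The case against.** The strongest reply is that later respiratory events do have a home. A reader might infer that respiratory depression is collected only in the PACU. The documents do not support that: Summary of Study Design records adverse events on days one to three, and ward respiratory depression needing naloxone is an adverse event on any ordinary reading. The plan also calls for side effects and any complications, and the protocol itself lists slowed breathing among methadone's side effects.

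Nor is the definition confined to the PACU. Potential Risks repeats the threshold without naming a setting: "If the patient goes into respiratory depression i.e., respiratory rate < 8 breaths per minute, naloxone". That passage, however, is treatment guidance and does not create a data item.

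Other parts of the reply also stand:

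- The protocol speaks of additional sedatives without saying where they are given. The link to the period after the PACU comes from reading Potential Risks together with Methods VII.
- Data collection is blinded and the same in every arm, and ketamine-only patients also receive narcotics afterwards, so under-recording need not differ by arm.
- Single-exponential decay is a simplification. The Background describes a tissue depot and a 6-8 hour duration of action.
- The investigators' data forms are not in the documents, so a field cannot be shown to be absent from them.

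The reply does not remove the difference in method. After the PACU, the written plan has no named respiratory item, no naloxone field and no rule for episodes between daily readings.

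**Conclusion.** The concern holds in a limited form. The explicit respiratory depression and naloxone item covers 4.2-12.5% of the first 24 hours. After that, ascertainment depends on general reporting and on daily readings that can miss a transient episode. This can under-count later events in the Objective 2 comparison.

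A reader might go further and conclude that the gap biases the comparison towards no difference, or try to put a number on the missed events. The first needs methadone-arm events to fall disproportionately after the PACU, which the stated half-life suggests but nothing in the documents quantifies. The second would require assuming both an event rate and that the general routes record nothing. Neither conclusion is supported.

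The result rests on the protocol's own PACU stay and half-life, and on reading the data list as written. Confidence is moderate, because the unseen data forms may already narrow the gap. The pain and opioid-consumption hypotheses and the sample size are unaffected. This is a cheap improvement to a safety comparison.

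**What to change.** In Patient Data Collection, IV (Postoperative data):

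- Apply the existing respiratory depression definition, unchanged, from PACU arrival through 72 hours or hospital discharge, whichever comes first.
- At 24, 48 and 72 hours, record yes or no with the time of the event, covering the whole interval since the last assessment and including any naloxone given. Take this from the ward vital-sign and medication records, not from the spot readings alone.
- Report PACU events, post-PACU events and the two combined, by arm.

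This concerns data collection only and changes nothing in clinical management. It adds a form entry and some chart abstraction per patient. Data Handling/Resourcing already gives the investigators access to medical records. The abstractor can stay blinded, because the ward records can be used without the anesthetic record that Methods II withholds from the data collector. The drawback is that ward charting is likely to be sparser than in the PACU, so some brief episodes will still be missed; reporting the two periods separately keeps that visible.

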STUDY PROPOSAL

**Intraoperative Ketamine and Methadone for
Laminectomy: Effect on Recovery, Postoperative Pain,
and Opioid Requirements**

IRB #: Pro00030109

NCT02252432

Date: 02/15/2020

**Intraoperative Ketamine and Methadone for Laminectomy: Effect on Recovery,
Postoperative Pain, and Opioid Requirements**

IRB #: Pro00030109

PRINCIPAL INVESTIGATOR

[name]., Ph.D.

CO-INVESTIGATORS

[name] [name].

INSTITUTION

Department of Anesthesiology
Cedars-Sinai Medical Center
[name]
[name]

E-MAIL

[contact]

[contact]

[contact]

STUDY OBJECTIVES

1. To determine if intraoperative double NMDA antagonism with ketamine + methadone reduces postoperative pain scores and opioid consumption more than single NMDA antagonism with ketamine or methadone alone after lumbar laminectomy.
2. To compare the side effects and hospital course between post-laminectomy patients receiving intraoperative ketamine + methadone vs. ketamine or methadone alone.

BACKGROUND & SIGNIFICANCE

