Test significance level, α	0.050	0.025	0.050	0.025
1 or 2 sided test?	2	2	2	2
Group 1 mean, μ_1				
Group 2 mean, μ_2				
Difference in means, $\mu_1 - \mu_2$	2.000	2.000	1.800	1.800
Common standard deviation, σ	2.000	2.000	2.000	2.000
Effect size, $\delta = \mu_1 - \mu_2 / \sigma$	1.000	1.000	0.900	0.900
Power (%)	80	80	80	80
n per group	17	21	21	25

Based on the power analysis, a sample size of 38 patients for each group will sufficiently allow us to detect at least a 30% reduction in postoperative opioid consumption and VAS pain scores with 80% power using a two sample t-test, significance level of 0.05 (two-sided). Total sample size will be 114.

ANOVA will be used to compare the continuous variables among the three treatment groups, and when significant differences are determined, a Newman-Keuls multiple-comparison test will be used to determine intergroup differences. Continuous data not normally distributed are analyzed by Kruskal-Wallis test, and when a significant difference is found, a Mann-Whitney U test is used for post-hoc comparisons between the intergroups. Chi-squared test (or Fisher's exact test) is used to analyze the categorical variables such as side effects and sex distribution.

INCLUSION & EXCLUSION CRITERIA

I. Inclusion criteria:

- 18 – 80 years old of either gender, scheduled for elective lumbar laminectomy

II. Exclusion criteria:

- ASA IV and above
- Intolerance, allergy, or contraindication to use of any medications used in this study
- Significant coronary artery disease (abnormal stress test, myocardial infarction within the last 3 months)
- Increased intraocular pressure (e.g., untreated glaucoma)
- Uncontrolled hypertension (BP > 140/90)
- Sleep apnea AND currently on continuous positive airway pressure (CPAP)
- Increased intracranial pressure or clinical signs thereof
- History of intracranial surgery, stroke, or brain aneurysm
- Cardiac arrhythmias particularly prolonged QT syndrome
- Drugs known to cause prolonged QT: class IA antiarrhythmics (quinidine, procainamide, dysopyramide), class III antiarrhythmics (sotalol, dofetilide, ibutilide, amiodarone), haloperidol, thioridazine, arsenic trioxide, HIV protease inhibitors, tricyclic antidepressants
- Individuals with significant psychological disorders including: schizophrenia, mania, bipolar disorder or psychosis
- Pregnant or lactating women
- Emergent laminectomy
- Those already receiving ketamine or methadone prior to surgery

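### The PACU hypoxemia item pools SpO2 below 90% with need for oxygen to stay above 95%, so it cannot separate desaturation from its management; the two limbs should be reported separately

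*Combined protocol and SAP*

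**What the plan says.** The item is in PATIENT DATA COLLECTION, IV. Postoperative data, among the PACU complications. Hypoxemia or desaturation is recorded if SpO2 is below 90%, "or need of supplemental oxygen to maintain" SpO2 above 95%. The protocol does not say how need is established: it gives no room-air check, duration, flow or time point.

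The same list has a separate entry for "respiration depression (respiratory rate < 8, need for naloxone, or respiratory arrest"), which contains no oxygen criterion. Respiratory distress is also listed separately.

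POTENTIAL RISKS describes what is done when a patient's respiratory rate falls below 8, and adds: "Supplemental oxygen will be provided to maintain oxygen saturation > 95% during these episodes". This is the only statement in the protocol about giving oxygen after surgery.

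These items feed the second study objective: "To compare the side effects and hospital course between post-laminectomy patients receiving intraoperative ketamine + methadone vs. ketamine or methadone alone". DATA ANALYSIS names the test: "Chi-squared test (or Fisher's exact test) is used to analyze the categorical variables such as side effects and sex distribution". It gives no event rate, margin or power for any safety outcome.

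**The concern.** One yes/no item joins a measured event to a treatment decision, and the two thresholds are five percentage points of saturation apart. A patient at 94% who is given oxygen to get above 95% is recorded exactly as a patient at 85%.

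The oxygen target also appears twice in different roles. POTENTIAL RISKS treats it as management of respiratory depression, while the data list treats it as a complication. An episode of slow breathing managed with oxygen can therefore add a hypoxemia event even if SpO2 never fell below 90%.

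What is at stake is how one line of the objective 2 safety table is read. The plan names respiratory depression as a methadone risk when further sedatives are given, so a reader will look to the hypoxemia row for supporting evidence. If many events in that row come from oxygen given at similar rates in every arm, a real difference in desaturation could be hidden. If the oxygen events differ by arm, an apparent difference could reflect mild need for oxygen and not desaturation. The pooled count cannot distinguish the two.

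**Working it through.** **The plan's own figure.** The only sample size basis is opioid consumption and pain scores: "Sample size estimates were based on the test for inequality of opioid consumption among the methadone, ketamine, and ketamine + methadone groups". For a difference of 15, SD 23, two-sided alpha 0.05 and power 0.80, the normal formula gives n = 2 × (1.960 + 0.842)² × 23² / 15² = 36.9. The t-test gives 37.9, rounded up to 38. The stated 38 per group reproduces, but it says nothing about hypoxemia.

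**Inputs for the check.** From the documents: 38 per arm, two-sided 0.05, chi-squared or Fisher's exact test. Assumed, because the documents give no such rates: a true SpO2 < 90% rate p in each arm, and a probability r that a patient is counted for oxygen regardless of desaturation. The comparison is one pair of arms.

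**Step 1, pooled rate.** q = p + (1 − p) × r. If r is equal in both arms, the risk difference shrinks by the factor (1 − r). With p = 25% and 5%, 20 points becomes 16 at r = 20% and 14 at r = 30%.

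**Step 2, power.** The arcsine approximation uses h = 2·arcsin√q1 − 2·arcsin√q2 and power ≈ Φ(h·√(38/2) − 1.96), plus the negligible opposite tail. For 25% vs 5%, h = 0.596, h·√19 = 2.60 and Φ(0.64) = 74%. Exact enumeration of the two named tests is alongside.

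| r, both arms | Pooled rates | Arcsine | Chi-squared, exact | Fisher, exact |
|---|---|---|---|---|
| 0 | 25% vs 5% | 73.8% | 74.0% | 61.0% |
| 20% | 40% vs 24% | 32.5% | 32.6% | 24.9% |
| 30% | 47.5% vs 33.5% | 23.9% | 23.4% | 17.0% |
| 50% | 62.5% vs 52.5% | 14.3% | 14.1% | 9.5% |
| 80% | 85% vs 81% | 7.5% | 7.6% | 4.2% |

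**Step 3, oxygen need that differs by arm.** Chi-squared, exact:
- 25% vs 5%, with oxygen counted in 30% vs 10%: pooled 47.5% vs 14.5%, power 90% (up from 74%).
- 25% vs 5%, with oxygen counted in 50% vs 30%: pooled 62.5% vs 33.5%, power 73% (about level).
- 20% vs 5%, with pooled rates assumed to be 60% vs 40%: power 42% (down from 55%).

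**Step 4, the strict limb at other base rates.** Chi-squared power at 38 per arm for SpO2 < 90% alone is about 14% for 10% vs 5%, 33% for 15% vs 5% and 55% for 20% vs 5%. By the normal approximation, 80% power would need about 435, 141 and 76 per group.

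**The case against.** The text says need of oxygen, not any oxygen given. Oxygen run as a precaution is, on a fair reading, not oxygen needed to hold a saturation. A reader might infer that routine PACU oxygen is counted as a complication. The documents do not support this: they describe no routine oxygen, and their one statement about giving it is tied to episodes of respiratory depression. What remains is narrower. Need has no recording rule, and even a true need at 94% is pooled with a reading of 85%.

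If oxygen follows respiratory depression, and methadone causes more of it, then oxygen need carries signal and pooling may help. Step 3 shows this can happen, so this part of the objection stands: neither the size nor the direction of the effect on power can be derived from the documents. It does not rescue the pooled item, because a single count cannot show which case occurred.

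The scope is also limited. Respiratory depression and respiratory distress have their own entries and are not touched. Low power for uncommon events comes first from 38 per group, and separating the limbs does not cure that.

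Finally, oxygen given to hold SpO2 above 95% can prevent a fall below 90%, so the strict limb alone could miss patients in difficulty. This is a sound reason to keep the combined item as well.

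**Conclusion.** This is a minor point of outcome definition, and it holds. One item in the objective 2 comparison mixes desaturation with a milder, treatment-based criterion that the protocol elsewhere lists as management.

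The possible cost is dilution if oxygen use is similar across arms. Under assumed rates of 25% vs 5%, power falls from about 74% to about 33% or 24% when 20% or 30% of every arm is counted for oxygen. This depends on the assumed rates and on oxygen being unrelated to arm. If oxygen need differs by arm, power can go either way.

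It would be tempting to conclude that the respiratory safety comparison loses most of its power. The documents do not support that. They give no hypoxemia or oxygen-use rates, they claim no safety power that could be lost, and the definition affects the hypoxemia item only.

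**What to change.** In the objective 2 safety comparison, tabulate and test two separate outcomes: SpO2 below 90%, and need for supplemental oxygen. Keep the combined item as a third row, so that patients whose desaturation was prevented by oxygen are still counted. The data form should record each limb with its own yes/no entry. PACU vital signs are already collected, and oxygen need is already part of the recorded complication.

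The cost is one or two more table rows with their tests, and fewer events in each separate outcome than in the pooled item. The change concerns recording and reporting only. It proposes no change to oxygen targets, monitoring or any other patient care.
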